### **Feasibility of Study Population Recruitment:**

At the UAMS Gynecologic Oncology clinic, approximately 160 new cases of endometrial cancer in obese women are seen each year (three new cases per week). The majority of these women are not diabetic at the time of the diagnosis of endometrial cancer. This represents the target population for this study. All new patients are seen by [name] or [name]. Except in rare circumstances, all these women will be scheduled for hysterectomy and bilateral salpingo-oophorectomy to stage their cancer. The typical time period between initially being seen by [name] or [name] and surgery is approximately 3 weeks. Thus, those women who agree to participate in this trial can begin the intervention with metformin and expect no delay to the time of their surgery.

### Study Calendar

Procedure	Pre-study	Study Period					Post-Operative clinic visit / Early Termination f
		Day 1 (Day of first dose)	Day 8			Days 14 -21 (Surgery)	
Eligibility Assessments							
Informed Consent	X						
Inclusion/Exclusion Criteria	X						
Medical History	X						
Study Assessments							
Physical Examination	X	X					
Physical Measurements e	X	X			X		
Demographics h	X						
Vital signs b		X					
Body Mass Index (BMI)	X				X		
Smoking Status	X						
Alcohol Status	X						
Concomitant Medications j	X	X	X k		X		
Adverse Events (AEs)		X	X k		X		
Telephone contact			X k				
Laboratory Test							
CBC Panel c	X				X		
Comprehensive Metabolic Panel	X				X		
Lipid Panel (Cholesterol, HDL-C, LDL-C, Triglycerides) *	X				X		
Urine Pregnancy Test d		X					
HbA1c *	X				X		
Study labs (send to [name] lab) g	X				X		
Clinical Drug Supplies							
Randomize		X					
Dispense study drug		X					
Dispense patient diary		X					
Review of drug diary			X k				
Collect unused study drug							X
Collect subject diary							X
Pathology							
Tumor Stage							X
Tumor Differentiation	X						X
Lymph Node Involvement							X
Tissue Collection (send to [name] lab)	X i				X		

\*Above standard of care (investigational-to be paid for by grant).

a A comprehensive panel will determine the following serum levels for the following: glucose, calcium, albumin, total protein, sodium, potassium, CO2, chloride, BUN, creatinine, ALP, ALT, AST, and total bilirubin (standard of care).

b Temperature, blood pressure, pulse, respiration rate.

c WBC, Platelets, Hb

d Within 7 days of randomization

e Physical measurements to include ECOG, performance status, weight and height (height only)

f Unused drug and diary to be collected during standard of care visit, no other research activities will be performed.

g Insulin, Leptin, Adiponectin, IGF-I and IGF-II

h Age, sex, race, and ethnicity

i If available

j Record concomitant medications that are actively being taken at time of consent till completion of study.

k Subjects receiving Metformin only

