## **Trial Objectives**

### **Primary Objectives**

1. To determine the effect of metformin on tissue markers of proliferation, apoptosis, and insulin-mediated signaling in endometrial cancer in non-diabetic obese women. Specifically, to determine the effect of metformin on the following tissue markers measured in tumor and adjacent non-tumor uterine (NTU) tissue:
  - a. Proliferation: Ki67, phosphorylated histone H3, estrogen receptor (ER), progesterone receptor (PR), and telomerase (hTERT).

- b. Anti-proliferation and apoptosis: PTEN, KLF9, cleaved caspase-3, and TUNEL staining.
  - c. Insulin-mediated signaling: total and phosphorylated versions of Akt, Erk1/2, AMPK, and receptors for Insulin, IGF-I, and IGF-II.
2. To determine the tolerability of a short course of metformin in non-diabetic obese women with newly diagnosed endometrial cancer.

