#### **F. Treatment modifications**

Patients will be monitored for their ability to tolerate the study medication during weekly follow-up telephone calls. If necessary, anti-diarrheal or anti-emetic therapy may be prescribed to ease any discomfort associated with the medicine. If a patient cannot tolerate the study medication and misses two or more doses in a row, they will be withdrawn from the study.

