#### **G. Subject removal**

Any patient who develops a grade 3 or higher gastrointestinal toxicity while on study will be discontinued. Subjects that withdraw from the study or that are withdrawn from the study due to unacceptable toxicity will return all unused study drug at their next scheduled clinic appointment.

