## **Outcome Measures**

### **A. The primary endpoints** of this study consist of the following:

- a. IHC-based tissue markers of proliferation: Ki67, phosphorylated histone H3, estrogen receptor (ER), progesterone receptor (PR), and telomerase (hTERT).
- b. IHC-based tissue markers of anti-proliferation and apoptosis: PTEN, KLF9, cleaved caspase-3, and TUNEL staining.
- c. IHC-based tissue markers of insulin-mediated signalling: total and phosphorylated versions of Akt, Erk1/2, AMPK, and receptors for Insulin, IGF-I, and IGF-II.
- d. Meformin-related adverse events.

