## Statistical Considerations

General approach: For each tissue endpoint, the tumor-NTU difference will be calculated in each patient as the paired difference in values between tumor and adjacent NTU tissue. For each blood endpoint, the endpoint response to treatment will be calculated in each patient as the paired difference between post-study and pre-study values. All data will be summarized by treatment arm as the mean, standard deviation (SD), median, and range, and will be graphed as box plots. Tumor-NTU differences and endpoint responses will be compared against zero via signed-rank test within each treatment arm. Treatment arms will be compared to each other for differences via Wilcoxon rank-sum tests, with additional details provided below. All statistical comparisons will be two-sided, and will employ a 10% alpha to reduce Type II error in this pilot proof-of-concept study.

Analysis plan for tolerability: Meformin-related adverse events will be summarized by type and treatment arm, both as proportions at each grade and as average grades (i.e., mean scores). For each type, the Wilcoxon rank-sum test will be used to compare treatment arms for differences in average grade.

Analysis plan for the IHC-based primary endpoints: The IHC-based primary endpoints will be measured in tissue, and will include markers of proliferation (Ki67, phospho-histone H3, ER $\alpha$ , PR, and hTERT), anti-proliferation and apoptosis (PTEN, KLF9, cleaved caspase-3 and TUNEL staining), and insulin-mediated signalling (total and phosphorylated versions of Akt, Erk1/2, AMPK, and receptors for Insulin, IGF-I, and IGF-

II). Endpoints measured in tumor tissue, adjacent NTU tissue, and tumor-NTU differences will be summarized and graphed as described above. Wilcoxon rank-sum tests will be used to compare endpoints measured in tumor, and likewise endpoints measured in adjacent NTU tissue, for differences between the metformin and no-metformin treatment arms.

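### No adverse-event assessment is scheduled at the post-operative/early-termination visit, so the primary tolerability endpoint can be incomplete for patients who stop metformin between checks

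*Protocol*

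**What the plan says.** **Endpoint.** The second primary objective (Protocol, Primary Objectives) is "To determine the tolerability of a short course of metformin in non-diabetic obese women with newly diagnosed endometrial cancer". The matching primary endpoint, item d under Outcome Measures, is "Meformin-related adverse events". Under Statistical Considerations, and identically in the SAP, AEs are summarised by type, arm and grade, and then: "For each type, the Wilcoxon rank-sum test will be used to compare treatment arms for differences in average grade".

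**Collection.** The AE row of the Study Calendar is marked on Day 1, at Day 8 and at surgery (Days 14-21). Footnote k restricts the Day 8 entry to "Subjects receiving Metformin only". The row is blank in the combined post-operative/early-termination column, where footnote f applies: "Unused drug and diary to be collected during standard of care visit, no other research activities will be performed".

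**Leaving treatment or study.** Section F (Treatment modifications) says: "If a patient cannot tolerate the study medication and misses two or more doses in a row, they will be withdrawn from the study". Section G (Subject removal) says: "Any patient who develops a grade 3 or higher gastrointestinal toxicity while on study will be discontinued".

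**Telephone contact.** Section E (Subject Diary) and Section F both describe weekly calls, to review the diary for compliance and to monitor tolerance respectively. The calendar shows one telephone contact, at Day 8, in the metformin arm only.

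**The concern.** The patients who say most about tolerability are those who stop because of the drug. If they are withdrawn before surgery, the only calendar column left to them is the one whose footnote excludes any AE assessment. The type of event may well be known by then. What has no scheduled place to be recorded is its highest grade, relatedness and outcome, and anything that appears or worsens after the last contact.

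The endpoint is analysed by grade, so an incomplete grade is an incomplete endpoint value. Withdrawal for metformin intolerance can arise only in the metformin arm, so this gap is not shared equally. Neither document states an AE collection window, a tolerability analysis set, or how withdrawn patients enter the comparison, so nothing downstream closes the gap. Reporting to the IRB does not close it either: for AEs it covers only those that are unexpected, related and add risk, and expected diarrhoea would not qualify.

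**Working it through.** **The plan's own figure.** The stated power of 91.6% (20 per arm, 1.0 SD, two-sided 10% alpha) reproduces. The Wilcoxon efficiency factor gives 20 × 3/π = 19.1 patients per arm, and a two-sample t-test with 19 per arm has 91.6% power. That figure does not depend on this point.

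**Scheduled AE checks, side by side.**

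| | Day 1 | Day 8 | Surgery, Days 14-21 | Post-operative / early termination |
|---|---|---|---|---|
| Metformin | yes | yes | yes | no |
| Control | yes | no | yes | no |

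After Day 1 the metformin arm has two scheduled AE checks and the control arm one. For a metformin patient the gaps between checks are 7 days (Day 1 to Day 8) and then 6 to 13 days (Day 8 to Days 14-21). At two doses a day, two consecutive missed doses amount to one day, so withdrawal can fall well inside either gap. The calendar's columns are displaced in the text copy, but footnote f states the restriction in words, so the reading does not hang on alignment.

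**Effect on an observed rate.** The Risks and Benefits section puts diarrhoea at 50%, which is 10 of 20. The documents do not give the number k of unrecorded events, so it is varied:

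- Counted as event-free, (10 − k)/20: 45%, 40%, 35%, 30% for k = 1 to 4.
- Excluded, (10 − k)/(20 − k): 47.4%, 44.4%, 41.2%, 37.5%.

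**Effect on the planned test.** Assumptions, none from the documents: 6/20 metformin and 1/20 control patients have a grade 2 event and everyone else is grade 0; w withdrawn metformin patients with events leave the analysis. With only two grade levels, the tie-corrected rank-sum statistic (normal approximation, no continuity correction) reduces to

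z = (p1 − p2) / √[K(N − K) / (n1·n2·(N − 1))],

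where p1 and p2 are the event proportions, K the total events and N = n1 + n2.

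| w | p1 | p2 | K, N | z | two-sided p |
|---|---|---|---|---|---|
| 0 | 6/20 = 0.300 | 0.050 | 7, 40 | 0.250/√(231/15600) = 2.05 | 0.04 |
| 1 | 5/19 = 0.263 | 0.050 | 6, 39 | 0.213/√(198/14440) = 1.82 | 0.07 |
| 2 | 4/18 = 0.222 | 0.050 | 5, 38 | 0.172/√(165/13320) = 1.55 | 0.12 |

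Scoring the lost patients as grade 0 gives 0.08 for one (0.20/√(204/15600), z = 1.75) and 0.16 for two (0.15/√(175/15600), z = 1.42). The plan does not say whether the test is exact or asymptotic. On two-level data the exact version equals Fisher's test and gives 0.091, 0.091 and 0.170 for w = 0, 1, 2. Either way, losing one patient leaves p under 0.10 and losing two takes it over.

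**The case against.** A reader might infer that the plan loses the worst tolerability observations and so favours metformin. The documents do not support that, for these reasons:

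- **Intolerance is monitored by other routes.** Section F provides weekly tolerance calls, and AEs are collected at the Day 8 contact.
- **The stopping event must be known for the rules to operate.** Discontinuing a patient for grade 3 gastrointestinal toxicity requires someone to have identified and graded it. The missed-dose rule requires knowledge of the intolerance.
- **Section G says only that such patients are discontinued.** It does not say that their AE assessment ends, whereas Section F does withdraw patients from the study.
- **Footnote f may be narrower than it reads.** The same column marks tumor stage, differentiation and lymph node involvement, which the Subject Data section lists as study data. It may bar extra procedures rather than all recording. AEs are also reviewed quarterly under Monitoring.
- **Ascertainment also runs the other way.** Day 8 collection in the metformin arm only gives that arm more opportunity to report AEs than controls.

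These points remove any claim of certain loss or known direction. They do not close the gap. The calls appear weekly in the text but once in the calendar. Section E describes its calls as a compliance review of a diary that holds dose dates and times, not symptoms. Knowing that a patient stopped is not the same as recording final grade, relatedness and outcome, and a plausible narrow reading of footnote f is not what it says.

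A second tempting inference is that events after surgery, lactic acidosis in particular, are a serious omission. This carries little weight. Dosing ends before surgery and later events are confounded with the operation. At the protocol's 3 per 100,000 patient-years, 20 patients over 21 days (20 × 21/365.25 = 1.15 patient-years) give about 0.00003 expected cases. Delayed or unresolved drug-related events would still lack scheduled capture.

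**Conclusion.** The concern holds as a risk of incomplete capture in a primary endpoint. The calendar schedules no AE assessment at the post-operative/early-termination visit and footnote f rules one out, so a metformin patient withdrawn between checks has no exit assessment. The calendar and the text also disagree on how often patients are called. How many events would be affected cannot be known from the documents, and many will be caught by the calls.

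The net direction of any bias is not established: possible under-recording among metformin patients who stop is set against more frequent questioning of that arm. The p-values (about 0.04, then 0.07 or 0.12) rest on assumed event rates, a single grade level, and complete loss of one or two patients. They show only that, with 20 per arm, two lost patients can move a comparison across the 10% threshold; they do not predict that this will happen. It is worth correcting because the remedy is cheap.

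**What to change.** 1. Amend footnote f and the AE row so that, in both arms, AEs since the last check are recorded at the existing post-operative/early-termination visit: type, grade, start date, relatedness and outcome.
2. Reconcile the single Day 8 telephone contact in the Study Calendar with the weekly calls in Sections E and F, and state the AE collection window.
3. State in the tolerability analysis, in both the protocol and the SAP, that withdrawn patients' events are included by randomised arm.

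This concerns data collection and analysis only; no treatment or stopping rule changes. The cost is a short amendment and one form at a standard-of-care visit that already takes place. The small downside is that some surgery-related events will have to be classified for relatedness.

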## Risks and Benefits

### A. Potential toxicities, risks and precautions

**Blood Samples:** Pain and bruising at the injection site and rare infections can occur. Experienced personnel will perform the phlebotomies using approved techniques. Pressure and dressings will be used to minimize pain, bruising and infection.

**Metformin Treatment:** Common (50% of the time): Diarrhea; Rare (10 – 25% of the time ): Nausea or vomiting, gas; Very rare (1 – 10% of the time): Weakness, indigestion, abdominal discomfort, headache, taste changes, abnormal stools, pain in the muscles, lightheadedness or dizziness, difficulty breathing, nail problems, increased sweating, flu-like symptoms, flushing, feeling of a fast beating heart.

**Very rare side effects include** Hirsutism (rare), lactic acidosis (3 cases per 100,000 patient years; 1) occurs most often in individuals with concomitant renal and liver disorders, 2) who are 80 years of age or older, 3) who have heart, liver or kidney failure, 4) who have a history of heavy alcohol intake.

### B. Potential Benefits

It is unknown if 14-21 days of metformin treatment will provide any therapeutic benefit. For this reason, there is no guaranteed personal health benefit for subjects participating in this study. However, information obtained from this study may improve prevention and treatment of endometrial cancer for individuals in the future.

## **Adverse Event Reporting**

All events listed below must be reported to the UAMS Institutional Review Board (IRB) within 10 days of the event or notification of event.

- 1). Local AEs that the investigator determines are:
  - a. Unexpected; and
  - b. Related to the research; and
  - c. Involve new or increased risks to subjects or others.
- 2). Any accidental or unintentional change to the IRB-approved protocol that place one or more subjects at increased risk or affects the rights and welfare of subjects or others.
- 3). Any new information that indicates an unexpected change to the risks or potential benefits of the research.
- 4). A breach in confidentiality that may involve risk to subject or others.
- 5). Any complaint of a participant that indicates an unanticipated risk or any complaint that cannot be resolved by the research team.
- 6). Incarceration of a subject.
- 7). Change in FDA labeling
- 8). Restrictions, terminations, or suspension of the study.
- 9). Premature completion.
- 10). Notifications of pending audits, inquiries or investigations by federal agencies.
- 11). Written reports from study monitor.

## **Ethical and Regulatory Considerations**

### **A. Recruitment**

Subjects will be recruited during clinic visits at the UAMS Gynecologic Oncology clinic.

### **B. Informed Consent**

Subjects will be consented for their participation in the study and the use of their data, tissues and blood samples for research purposes. The principal investigator (PI), a sub-investigator or a designated staff member will discuss the informed consent form with the potential subject. The consent process will take place in a quiet and private room. Subjects may take as much time as needed to make a decision about their trial participation and may take the document home if desired. An interpreter will be utilized if native language is a barrier to understanding the consent form. The individual

obtaining consent will thoroughly explain each element of the document and outline the risks and benefits, alternate treatment(s), and follow-up requirements of the study. Participation privacy will be maintained and questions regarding participation will be answered. No coercion or undue influence will be used in the consent process. No research related procedures will be performed prior to obtaining informed consent. All signatures and dates will be obtained. A copy of the signed informed consent form will be given to the subject. The informed consent process will be documented in each subject's research record.

### **C. Protocol Management**

Study management will be handled by the Cancer Clinical Trials Office (CCTO) in the Winthrop P. Rockefeller Cancer Institute.

### **D. Drug Accountability**

Drug supplies will be kept in a secure, limited access storage area under the recommended storage conditions in the research pharmacy in the Winthrop P. Rockefeller Cancer Institute under the direction of the research pharmacist.

## **Outcome Measures**

### **A. The primary endpoints** of this study consist of the following:

- a. IHC-based tissue markers of proliferation: Ki67, phosphorylated histone H3, estrogen receptor (ER), progesterone receptor (PR), and telomerase (hTERT).
- b. IHC-based tissue markers of anti-proliferation and apoptosis: PTEN, KLF9, cleaved caspase-3, and TUNEL staining.
- c. IHC-based tissue markers of insulin-mediated signalling: total and phosphorylated versions of Akt, Erk1/2, AMPK, and receptors for Insulin, IGF-I, and IGF-II.
- d. Meformin-related adverse events.

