#### **E. Subject Diary**

A subject who is randomized to metformin will receive a diary on Day 1. The subject is to record the date and time of self-administration of the study drug. The diary will be reviewed weekly by members of the study team via telephone for compliance. The diary will be collected at the subject's post-operative visit.

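### Tolerability of the metformin course is a primary objective, but it is measured only by type and grade of adverse event, so courses with very different completion can give the same result

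*Protocol*

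**What the plan says.** Protocol, Primary Objectives, item 2: "To determine the tolerability of a short course of metformin in non-diabetic obese women with newly diagnosed endometrial cancer".

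Protocol, Outcome Measures, A, item d is the only endpoint that answers to it: "Meformin-related adverse events". The secondary endpoints add no measure of completion, discontinuation or adherence.

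Protocol, Statistical Considerations, tolerability paragraph: the events are to be "summarized by type and treatment arm, both as proportions at each grade and as average grades (i.e., mean scores"), and then "For each type, the Wilcoxon rank-sum test will be used to compare treatment arms for differences in average grade". The SAP repeats this paragraph and adds nothing to it.

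Elsewhere the Protocol sets out how patients come off drug and what is known about their dosing:

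- Trial Design, F: "If a patient cannot tolerate the study medication and misses two or more doses in a row, they will be withdrawn from the study". This requires intolerance and missed doses together, and it names no grade.
- Trial Design, G: "Any patient who develops a grade 3 or higher gastrointestinal toxicity while on study will be discontinued". The same section also recognises patients who withdraw themselves.
- Trial Design, E, for the metformin arm: "The subject is to record the date and time of self-administration of the study drug". The diary is reviewed weekly by telephone.
- The Study Calendar schedules collection of the diary, unused drug and concomitant medications. Section F permits anti-diarrheal and anti-emetic treatment.

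Neither analysis plan uses the diary, the returned drug, the withdrawals or the supportive treatment.

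**The concern.** Whether patients tolerate a course depends on what they experience and on whether they can finish it. The plan measures the first and leaves out the second, although its own withdrawal rule in section F turns on the second.

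Under the planned analysis, a woman who stops in the first week with grade 2 diarrhea counts the same as one who has grade 2 diarrhea and takes every dose up to surgery. A woman who stops because she cannot bear the tablets, with no graded event recorded, counts as grade 0. Supportive treatment may also lower a recorded grade, and its use is not reported beside the grades.

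The trial could therefore report a favourable result on a primary objective for a course that a material share of patients did not finish. The Protocol says the results will be used to apply for further funding, so the next study's designers would want to know how many patients stopped and why.

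**Working it through.** **The plan's own figure.** The only computed figure in the statistical sections is 91.6% power for a 1.0 SD difference, 20 per arm, two-sided 10% alpha. Using the rank-sum test's efficiency under normality, 20 × 3/π = 19.1 patients per arm. The noncentral-t calculation at 19 per arm gives 91.60%. The figure reproduces, and this point does not affect it.

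**Inputs for the illustration.** From the documents: 20 metformin patients, and the tolerability summaries quoted above. Assumed: 8 of the 20 have grade 2 diarrhea and 12 have none, and withdrawn patients stay in the denominators. The documents give no stopping rate and define no analysis population, so these are illustrative choices.

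**Scenario A: all 8 finish. Scenario B: all 8 are withdrawn under section F.**

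| Quantity | A | B |
|---|---|---|
| Proportion at grade 0 | 12/20 = 60% | 12/20 = 60% |
| Proportion at grade 2 | 8/20 = 40% | 8/20 = 40% |
| Mean grade | (8 × 2)/20 = 0.8 | (8 × 2)/20 = 0.8 |
| Grades entering the rank-sum test | twelve 0s, eight 2s | twelve 0s, eight 2s |
| Completion | 20/20 = 100% | 12/20 = 60% |

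The rank-sum statistic depends only on the grades. Against any given control arm, A and B therefore give the same p-value. This holds for any number of patients withdrawn with grade 1-2 events, because completion appears nowhere in the planned analysis.

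**Where the blind spot ends.** Suppose instead the 8 stop for grade 3 gastrointestinal toxicity under section G, and the events are judged metformin-related. The mean grade becomes (8 × 3)/20 = 1.2 and the table shows 8/20 = 40% at grade 3. That kind of stopping is visible. What is not visible is section F withdrawal with grade 1-2 or ungraded complaints, and self-withdrawal.

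**What a stopping proportion would deliver with 20 patients.** Exact (Clopper-Pearson) 95% limits for k of n stopping are: lower = Beta quantile 0.025 with parameters (k, n−k+1); upper = Beta quantile 0.975 with parameters (k+1, n−k).

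| Stopping | Estimate | 95% CI |
|---|---|---|
| 0/20 | 0% | 0-17% |
| 4/20 | 20% | 6-44% |
| 8/20 | 40% | 19-64% |

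The intervals for 0/20 and 8/20 do not overlap (17% against 19%). The interval for 4/20 overlaps both.

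**The case against.** The strongest reply is that type, frequency and grade of drug-related events, set against a concurrent untreated arm, already is a tolerability measure. Grade 3 or higher gastrointestinal events appear in it directly. The trial is a small pilot, and the diary and unused drug are collected anyway, so completion could be tabulated afterwards. Making completion the lead measure would be partly a matter of preference, and the documents set no acceptable rate against which to judge it.

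Much of this stands. The planned summary is informative but incomplete, and completion should sit beside the grades without replacing them. What does not stand is the appeal to later recovery. The quantity belongs to a primary objective, and its definition, denominator and reasons for stopping should be fixed before the data are seen. The list of recorded data in Trial Design, D contains no dosing or stopping item.

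A reader might infer several stronger things that the documents do not support:

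- **That the plan cannot address tolerability, or that no stopping would show.** Both are contradicted by the grade proportions.
- **That two missed doses alone mean intolerance.** Section F requires both conditions.
- **That many or most patients will stop.** The Risks and Benefits section gives diarrhea as occurring 50% of the time, but at no stated grade and with nothing on stopping. Study Drug lists it only as above 10%.
- **That a null marker result could not be interpreted.** The diary data would exist. Adherence in the marker analysis is a separate question.

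**Conclusion.** The point holds as a gap in the definition of a primary endpoint. The planned tolerability result does not change with withdrawals that occur at grade 1-2, without a graded event, or by the patient's own choice. In the illustration, completion of 20/20 and of 12/20 give the same mean grade of 0.8, the same grade proportions and the same rank-sum result.

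The counts are assumed, and the identity needs withdrawn patients to be kept in the denominators. A reader might go further and infer that early stopping would improve the score, because no adverse-event assessment is scheduled at the early-termination visit. The documents do not say that withdrawn patients are dropped or that their earlier events are discarded, so that remains a possibility only.

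The plan can return the same result for courses with very different completion; it need not. Sample size and power are unaffected.

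**What to change.** In the Protocol (Outcome Measures, A, item d, and the tolerability paragraph of Statistical Considerations) and in the same paragraph of the SAP, add the following.

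1. Among all patients randomised to metformin, the proportion who permanently stop metformin before the end of their own planned pre-surgery course, for any reason, with an exact binomial interval. Break this down by reason: withdrawal under section F, discontinuation under section G, self-withdrawal, other. Using each patient's own planned course, and not a common 14-day minimum, captures stopping between day 14 and surgery.
2. Diary-recorded doses taken over doses scheduled from Day 1 to the patient's planned last dose before surgery.
3. Use of anti-diarrheal or anti-emetic treatment.

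Add these items, including the planned last-dose date and the reason for stopping, to the recorded data in Trial Design, D. Report the stopping proportion alongside the type and grade summaries and draw the tolerability conclusion from both. The stopping criteria themselves do not change.

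The cost is wording in both documents, a few recorded items and one table. The diary and concomitant medications are already collected, and no visit or patient is added. The downsides are a wide interval with 20 patients and a tolerability statement that may be less favourable.
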